3.3 RISK/BENEFIT ASSESSMENT

3.3.1 POTENTIAL RISKS

Modification of the ETT design to prevent microaspiration (CASS-ETT) is one of several approaches to VAP prevention. ETTs that allow continuous aspiration of subglottic secretions or are equipped with PU cuff have been investigated in several randomized trials, with the weight of evidence suggesting a reduction of VAP associated with this intervention. The EVAC-PU-ETT has been recommended or suggested for use as a VAP preventative strategy by the American Thoracic Society and the Centers for Disease Control and Prevention. The EVAC-PU-ETT has been clinically used at many institutions to prevent VAP. However, there has been no systematic prospective study of the EVAC-PU-ETT to evaluate for both the efficacy of the tube for the prevention of VAP and for the safety of the tube as compared to a standard ETT to ensure there is no higher risk of airway injury related to subglottic suctioning.

Our previous pilot prospective randomized trial did not establish differences in risks between the PVC-ETT and the EVAC-PU-ETT. It remains uncertain if the EVAC-PU-ETT which has been demonstrated as a strategy for VAP prevention is also as safe as the standard ETT. There is equipoise to address the study question as there is insufficient evidence to claim one type of ETT is more effective and safe than another at preventing VAP.

This comparative effectiveness trial is designed to provide more rigorous effectiveness and safety evaluation of the EVAC-PU-ETT. We hypothesize the modified ETT with subglottic suctioning reduces the occurrence of VAP, is as safe as the PVC-ETT and does not pose an increased risk of laryngeal and/or tracheal injury.

The PVC-ETT and the EVAC-PU-ETT are FDA-cleared for clinical use (tracheal intubation). They will be used in this study in accordance with their FDA-cleared clinical indications and manufacturer recommendations. The use of these ETTs are considered medically recognized standards of care (see Appendix III for the ETT product labels).

It may be difficult to differentiate side effects of the ETT from complications patients who undergo intubation experience regardless of the type of ETT used. The product labels for both ETTs show no differences in the type, nature, or severity of complications between the tube types. Device-related complications are considered the same. Some subjects will receive the EVAC-PU-ETT and they would not otherwise receive this ETT type outside of the study. However, both ETTs we will use are medically recognized standards of care and there is no known differential in risk between the two treatments.

From clinical experience, it is expected that the EVAC-PU-ETT is as safe as the PVC-ETT. For these reasons, we believe that subjects enrolled in this study will be exposed to the same risks if they were outside of the study.

This study will specifically evaluate the following immediate, short, and long-term device-related complications involving laryngeal anatomy and function that are also outlined in the product labeling:

Immediate risks:

- Airway complications at the time of tube insertion
- Need to change/reduce the pre-assigned size of the tube

Short-term risks:

- Stridor immediately after extubation
- Requirement for stridor treatment
- Reintubation within 24 hours due to upper airway complications such as stridor or obstruction

Long-term risks (6 months after extubation as identified by a phone interview)

- Tracheostomy
- Persistent throat discomfort or pain
- Stridor
- Residual hoarseness or change in voice (dysphonia)
- Dyspnea
- Whether dyspnea symptoms are attributable to upper or lower airway disease (certainly due to upper airway, probably, possibly, or unrelated).

Section 9.2 outlines how the study team will assess airway complications for safety of the ETT type during the study.

We do not expect differences in risks at insertion between the PVC-ETT and the EVAC-PU-ETT. However, while the tubes have the same internal diameter, the EVAC-PU-ETT tube has a slightly larger external diameter (due to the additional port) which effectively increase the outer diameter by 0.5 points. This may mean a different tube is requested prior to the intubation attempt or it is requested after a failed attempt is made. If this happens because the outer diameter of the tube is thought to be a problem, a non-study tube will be used. Specifically, if a <7.0 size is needed, then it will not be a study tube since alternative sizes are not available for this study. We will monitor insertion complications, including the need to insert smaller size tubes.

Complications related to mechanical ventilation are not research risks and are instead due to standard of care which subjects would be exposed to outside of the study. However, certain symptoms, like dyspnea, will not be distinguishable between device and ventilator. Assessment of risks will primarily focus on complications to upper airway which are more closely related to the breathing device than the ventilator use. For the trial, we will document whether the symptoms are thought to be related to upper vs lower airway dysfunction (evidence of pulmonary disease or condition), and we will compare the frequency between the two groups.

This study will evaluate cognitive function. We do not expect cognitive changes to represent side effects of the ETT. We hypothesize that decreased cognitive function is a consequence of infection (VAP) as a result of neuroinflammation. We hypothesize that patients that do not experience infection or hypoxemia resulting from pneumonia should have less cognitive dysfunction. If the EVAC-PU-ETT is protective from VAP, then the intervention group should also have less cognitive dysfunction. Therefore, side effects of cognitive dysfunction are not research risks, and are instead risks of the condition they would be exposed to outside of the study.

This study increases the risk of invasion of privacy as patients will be enrolled into this emergency medicine study without his or her consent. We anticipate most subjects will be enrolled in the study under a waiver of consent because this patient population may not immediately have the capacity to provide consent to be in the study.

3.3.2 POTENTIAL BENEFITS

The intervention ETT is known to prevent ventilation associated pneumonia (VAP). This study will allow for the controlled evaluation of the comparative effectiveness and safety of a polyurethane-cuffed endotracheal tube with subglottic suctioning for prevention of VAEs. There are several benefits that could result from this research for the subjects, their family, as well as society. The greater benefit for the subject would be a reduction in the incidence of VAP (some patients may not develop VAP as a result of the intervention), with a resulting reduced duration of mechanical ventilation, length of stay, and cost, with no increased safety issues identified. All these outcome benefits will result in a reduction in institutional and societal costs. Indirect benefits will be shared by family members and society as a whole.

4 OBJECTIVES AND ENDPOINTS

Primary Aims (Objectives)	Primary Specific Aim: We will determine if EVAC-PU-ETT is as safe as PVC-ETT and if long-term patient quality of life and cognitive function are better in EVAC-PU-ETT, compared with PVC-ETT. As primary effectiveness endpoint, we will determine if the effect of EVAC-
----------------------------------	--

	
PU-ETT on quality of life (physical and mental component summary), as measured by the 36-item Short-Form General Health Survey, is better compared with PVC-ETT, at 6 months after randomization. An additional patient-centered endpoint will be the proportion of patients cognitively impaired, assessed by the National Alzheimer Coordinating Center's Uniform Data Set.

Secondary Aims (Objectives)	
Secondary Specific Aims: We will determine if EVAC-PU-ETT is as safe as PVC-ETT. We will also determine if EVAC-PU-ETT reduces Infection Related Ventilator-Associated Complications (IVACs) and is more cost effective than PVC-ETT.
 
Aim 1. For our safety endpoint, we will evaluate the safety profile of EVAC-PU-ETT based on airway-related complications, compared with the PVC-ETT, at 6 months after randomization.
 
Aim 2. To determine if the EVAC-PU-ETT is effective in reducing the incidence of Center for Disease Control (CDC)-defined IVACs and Ventilator-Associated Events (VAEs) compared with PVC-ETT.
 
Aim 3. To perform economic evaluation (cost-consequence approach) of quality of life of patient and the healthcare resource utilization and cost for hospitals of EVAC-PU-ETT compared with PVC-ETT.

Primary Endpoints	
The study primary endpoints will be measures of quality of life, and cognitive function at 6 months after randomization.
 
Quality of life. The patient interview will also include the evaluation of quality of life using the RAND version 1.0 of the Medical Outcomes Study 36-item Short-Form (SF-36) General Health Survey. This instrument includes eight sub-indices of the following types: vitality, physical functioning, bodily pain, general health perceptions, physical role functioning, emotional role functioning, social role functioning, and mental health. It also includes a single item that provides an indication of perceived change in health.
 
Cognitive function. At the six-month follow up, we will also assess cognitive function using a battery of tests assessing domains previously demonstrated to be potentially affected by periods of respiratory distress and validated in both normal aging and cognitively impaired populations. The core battery will consist of measures from the National Alzheimer Coordinating Center's Uniform Data Set (UDS): 1) Montreal cognitive assessment (MoCA), a global cognitive screen which has been shown to be much more sensitive than the Mini Mental Status Examination; 2) Craft Story Recall (an analogue to the Logical Memory subtest of the Wechsler Memory Scale), measuring immediate and delayed verbal contextual recall; 3) Benton Complex Figure test, which measures executive function and visuospatial ability, as well as

	
visuospatial recall; 4) Digit Span, a test of attention and working memory; 5) Trail Making, Parts A and B, measures of attention and divided attention/working memory; and 6) semantic and phonemic verbal fluency test. Advantages of using the UDS are that it contains tests sensitive to cognitive impairment following respiratory illness that have been validated in older impaired and unimpaired populations, is freely available via the National Alzheimer Coordinating Center website, provides normative data and a normative calculator that are easily accessible online, and permits comparison with a nationwide database of older adults. Additional tests will be included to ensure specific impairments in patients with respiratory illness are adequately assessed: 1) Hopkins Verbal Learning Test-Revised – HVLT-R), a measure of declarative verbal list learning and memory, which allows evaluation of the participant's ability to use semantic clustering strategies during recall, which may be disrupted following acute or prolonged respiratory illness; 2) Coding (previously termed "Digit symbol", from the Wechsler Adult Intelligence Scale-4th ed [WAIS-IV], 2008, PsychCorp), a measure of speed of information processing /working memory. Participants will be considered cognitively impaired if any test is 2 standard deviations or greater below the age, sex, education adjusted mean, or if two tests are 1.5 standard deviations or greater below the mean, consistent with previous studies in this area. As we will not have access to neuropsychological tests prior to illness, we will include a measure of premorbid ability, the Test of Premorbid Functioning (TOPF, 2009, PsychCorp), in order to gauge whether current performance on cognitive measures may represent a change from previous levels of function.

Secondary Endpoints	
Safety. Safety endpoints include clinical measures intended to evaluate the direct effect of the device at the site of placement. To evaluate the effect of the ETT at the local level we will be assessing subjective and objective measures of laryngeal anatomy and function, in addition to any device-related adverse events. We will record: 1) airway complications at the time of ETT insertion; 2) the presence of cuff leak test prior to study ETT removal, as indicated by a difference between the inspiratory tidal volume (measured before cuff deflation) and the expiratory tidal volume (measured after cuff deflation) of at least 10% or >110 mL; 3) stridor immediately after extubation; 4) requirement for stridor treatment (racemic epinephrine, helium-oxygen gas mixture); or 5) reintubation within 24 hours due to upper airway complications such as stridor or obstruction. Long-term safety will be assessed by ascertaining the persistence of airway sequelae six months after randomization using a standardized questionnaire via in-person interview. Data collected include the presence of persistent throat discomfort or pain, residual hoarseness, change in voice, and dyspnea.
 
The main secondary clinical efficacy endpoint will be the incidence of CDC defined Infection-Related Ventilator-Associated Complications (IVAC)


occurring during the ICU stay from enrollment until ICU discharge. An IVAC event is defined by a 14-day period, starting on the day of onset of worsening oxygenation. For this study, we will use the CDC proposed tiered approach algorithm that encompasses ventilator associated conditions (VAC), infection related ventilator-associated complication (IVAC), and possible VAP.
 
Step 1: VAC (≥1 required):
 
 1) Daily min FiO_2 increase ≥ 0.20 (20 points) for ≥ 2 days - OR 2) Daily min PEEP increase $\geq 3 \text{ cm H}_2\text{O}$ for ≥ 2 days (after two days of stable or decreasing daily minimum values) 
Step 2: IVAC:
 
 1) Temperature $>38.0^\circ\text{C}$ OR $<36.0^\circ\text{C}$ - OR 2) White blood cell count $\geq 12,000$ or $\leq 4,000 \text{ cells/mm}^3$ - AND 3) A new antimicrobial agent is started and is continued for ≥ 4 days. 
Step 3: Possible VAP:
 
Criterion #1: Positive cultures of one of the following specimens collected within $+\/- 2$ days of onset of VAC, meeting quantitative or semi-quantitative thresholds, without requirement for purulent respiratory secretions: 1) Endotracheal aspirate; 2) Bronchoalveolar lavage; 3) Protected specimen brush; 4) Lung tissue - OR
 
Criterion #2: Purulent respiratory secretions AND a positive culture of one of the following specimens (qualitative culture, or quantitative/semi-quantitative culture without sufficient growth to meet Criterion #1): 1) Sputum; 2) Endotracheal aspirate; 3) Bronchoalveolar lavage; 4) Lung tissue; 5) Protected specimen brush.
 
Other secondary endpoints related to VAP
 
 1) Incidence of ventilator-associated events (VAEs); 2) Respiratory antimicrobial use; 3) VAP risk using a "clinical" definition for interpretation of the study findings in the context of previous literature where clinical definitions were used; 4) Occurrence of early- versus late-onset IVAC and time to first IVAC event. Early-onset IVAC is defined as IVAC occurring within four days of tracheal intubation while late-onset VAP is defined as VAP occurring 5 days or later. 
Additional secondary clinical endpoints
 
 1) 28-day ventilator-free days; 2) Daily Sequential Organ Failure Assessment (SOFA) score; 3) Length of ICU and hospital stay; 4) In-hospital and 6-month mortality comparison between the two groups.

5 STUDY DESIGN

5.1 OVERALL DESIGN

This will be a single-site randomized, controlled, phase 2 trial, conducted under EFIC, comparing the safety, long-term patient quality of life, and cognitive function of patients who undergo emergency tracheal intubation with one of two different ETTs, one of which is designed specifically to prevent VAP: 1) An ETT with a PU cuff that is also fitted with a lumen to allow continuous subglottic suction (EVAC-PU-ETT); and 2) A standard ETT with a PVC cuff (PVC-ETT). 1,074 adult patients requiring endotracheal intubation in the Emergency Department (ED) or hospital setting for acute respiratory failure will be randomly assigned in an equal fashion to be intubated with one of the two ETTs. The first 90 patients have been randomized at OHSU and have completed study follow-up procedures, while the remaining 984 will be randomized at YNHH. Activities conducted at the first clinical site were overseen by the OHSU IRB. After closing enrollment at OHSU, the study will enroll participants at YNHH only. The trial will be overseen by the Yale IRB, including review of all Community Consultation and Public Disclosure activities, and oversight for the Public Disclosure activities in the Portland area at the conclusion of the study.

Because endotracheal intubation is performed in an emergency setting, the unit of randomization will be the intubation kits containing, in a concealed manner, one of the two types of ETT. The intubation kits are placed in areas where emergency intubation teams receive their intubation equipment supplies. In order to maximize the potential benefit of the modified ETT for the prevention of VAP, it is imperative that the tubes be available to the entire at-risk population. The study is designed to allow all patients requiring emergency intubation to be potentially eligible for enrollment to ensure the applicability of the study findings to a generalizable setting of patients receiving emergency intubation for respiratory failure or airway protection.

Surveillance for VAP will occur while patients are in the ICU until extubation, ICU discharge or death. A large proportion of patients is expected to be extubated within 48 hours. Although patients with early extubation are not considered to be at risk of VAP, they will be included in the study to adhere to the intent-to-treat approach, considering that the patient has been randomly assigned to one of the study treatment arms. Throughout the patient's hospitalization, data will be collected continuously from the time of randomization until hospital discharge or death.

The study will use clinical measures to address device safety and consequences of VAP reduction on long-term, patient-centered outcomes. At six months post randomization, all patients will have a structured in-person interview to screen for the presence of and assess airway symptoms or persistent sequelae of laryngeal dysfunction. Any need for consultation of a specialist for airway complaints will be recorded and information abstracted from the medical record, if appropriate. During the interview, we will record clinical measures intended to evaluate safety, quality of life, and cognitive function. If a visit

to a specialist for evaluation and/or treatment of speech, swallowing, or breathing problems occurred, the medical record will be reviewed. Data pertinent to the continuing adverse event will be abstracted from the medical record.

Although randomization assignment occurs in a double-blind fashion, the study will subsequently be single-blind. Due to the different devices used and the presence of suctioning, it will not be possible to maintain the study as double-blind. To protect the integrity of the study from unmasking of investigators other than the primary caregivers, the adjudication of the VAP will follow an algorithmic, data-driven, objective approach. Likewise, the follow up airway assessment will occur in a blinded fashion. The statistician will be blinded to the randomization assignment, by labeling the randomization assignment as device A or B.

One interim analysis will be conducted when approximately 50 percent of the total sample has been collected. For details on planned interim analyses see **Section 9.4.6, Planned Interim Analysis**.

5.2 SCIENTIFIC RATIONALE FOR STUDY DESIGN

The proposed study will be a randomized, controlled trial, conducted under Exception From Informed Consent (EFIC), comparing patients who undergo emergency tracheal intubation with one of two different ETTs, one of which is designed to prevent VAP: 1) An ETT with a PU cuff that is also fitted with a lumen to allow CASS (EVAC-PU-ETT); and 2) A standard ETT with a PVC cuff (PVC-ETT). Approximately 1,074 adult patients requiring endotracheal intubation in the ED or hospital for acute respiratory distress or failure will be randomly assigned in an equal fashion to be intubated with one of the two ETTs (537 patients in each group). Because endotracheal intubation is performed in an emergency setting, the unit of randomization will be the intubation kits containing, in a concealed manner, one of the two types of ETT. The intubation kits are placed in areas where emergency intubation teams receive their intubation equipment supplies. In order to maximize the potential benefit of the modified ETT for the prevention of VAP, it is imperative that the ETTs be available to the entire at-risk population. Thus, given that a sizable proportion of patients that undergo tracheal intubation and mechanical ventilation are intubated in the ED, it is important to include this cohort in the study population. The study is designed to allow all patients requiring emergency intubation to be potentially eligible for enrollment to ensure the applicability of the study findings to a generalizable setting of patients receiving emergency intubation outside the operating room. The study ETT will be concealed and packaged in opaque sealed envelopes so that the assignment will occur in a blinded fashion. The study ETTs will be provided in three internal diameter sizes: 7.0 mm, 7.5 mm, and 8.0 mm. Unless otherwise indicated, the size recommendation will be I.D. 7.0 for women, I.D. 7.5 for men, and I.D. 8.0 as clinically indicated. Non-study ETTs will be also available for use in protected populations, for patients with exclusion criteria, and for participants declining participation. The kits will be distributed by the research team to the ED and area airway carts.

5.3 JUSTIFICATION FOR DEVICE

We conducted an extensive literature review and meticulously examined the strengths and weaknesses of previous trials. We also took advantage of lessons learned from our own pilot trial. Taking into account all considerations above, we have determined that the best ETT candidate device associated with the highest potential of performing effectively in preventing microaspiration and demonstrating the highest safety profile is the CASS-ETT with PU cuff material. Our central hypothesis is that EVAC-PU-ETT is safe and superior to the standard PVC-ETT in reducing the occurrence of VAP and several of its long-term consequences. There is high potential to minimize the risk of VAP when consistently applying a VAP prevention bundle combined with the use and proper management of a specialized ETT. Since it is important to definitively determine the role of the device, for the intervention we chose the ETT with the highest potential of reducing microaspiration.

5.4 END OF STUDY DEFINITION

At 6 months post-randomization, study participants will be evaluated in person either at our research facility space or at their residence for airway evaluation and related disorders, quality of life and cognitive impairment. A participant is considered to have completed the study if he or she has completed all phases of the study including the last visit shown in **Section 2.3, Schedule of Activities (SOA)**.

The end of the study is defined as completion of the 6 month in-person follow-up visit.

6 STUDY POPULATION

6.1 INCLUSION CRITERIA

In order to be eligible to participate in this study, an individual must meet all of the following criteria:

1. ≥ 18 years of age
2. Requiring emergency endotracheal intubation in the ED or in-hospital for acute respiratory distress or failure
3. A study intubation kit containing the study ID number must have been used for the emergency intubation
4. Admitted to the ICU and receiving mechanical ventilation

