
Safety. Safety endpoints include clinical measures intended to evaluate the direct effect of the device at the site of placement. To evaluate the effect of the ETT at the local level we will be assessing subjective and

objective measures of laryngeal anatomy and function, in addition to any device-related adverse events. We will record: 1) airway complications at the time of ETT insertion; 2) the presence of cuff leak test prior to study ETT removal; 3) stridor immediately after extubation; 4) requirement for stridor treatment (racemic epinephrine, helium-oxygen gas mixture); or 5) reintubation within 24 hours due to upper airway complications such as stridor or obstruction. Long-term safety will be assessed by ascertaining the persistence of airway sequelae six months after randomization using a standardized questionnaire via in-person interview. Data collected include the presence of persistent throat discomfort or pain, residual hoarseness, change in voice, and dyspnea.

VAE: The trial will use CDC-defined Ventilator-Associated Events (VAEs). The tiered CDC approach includes the identification of ventilator associated conditions (VACs) in the first step, the presence of fever or increased white blood count and the initiation of new antimicrobial in the second step (IVAC), and documentation of a respiratory source of infection in the third step (possible ventilator associated pneumonia - VAP).

Study Population:

An estimated 1,074 patients will be enrolled in the study. Those eligible to participate in the trial are adult patients (older than 18 years of age) requiring emergency endotracheal intubation in the ED or in the hospital for acute respiratory distress or failure resulting in the requirement for Intensive Care Unit (ICU) admission and mechanical ventilation.

Inclusion criteria

Subjects eligible to participate in the trial are adult patients (18 years of age or older) requiring emergency endotracheal intubation in the ED or in-hospital for acute respiratory distress or failure resulting in ICU admission and mechanical ventilation. For a patient to be enrolled in the trial, a study intubation kit containing the study ID number must have been used for the emergency intubation.

[figure not shown]
Exclusion criteria

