6.3 SCREEN FAILURES

Screen failures are defined as participants meeting inclusion criteria but who have a study ETT inserted in a condition or situation meeting one or more of the exclusion criteria listed in **Section 6.2, Exclusion Criteria**.

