7 STUDY INTERVENTION

7.1 STUDY INTERVENTION(S) ADMINISTRATION

7.1.1 SCREENING AND ENROLLMENT

Potential subjects enrolled will be identified through a three-prong process: 1) An automatically generated report listing all new patients admitted to the ICU and receiving mechanical ventilation will be generated daily. All patients listed in the report will be reviewed at the bedside to determine the presence of a study ID bracelet and confirm that a study device was inserted; 2) Self-addressed envelopes for campus mail to the study team provided in the intubation kits and containing the

participant identification information; and 3) Used intubation kits deposited in return bins located in the ED and ICUs will be scanned for tracking and reconciliation of all study devices. In our previous pilot study experience, these strategies allowed 100% success tracking study devices and participants.¹⁰⁶ After identification, study personnel will approach the participant or authorized representative to obtain informed consent for continued study participation.

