9.3.5 ADVERSE EVENT REPORTING

For the duration of patient therapy, the investigators will be responsible for monitoring and recording 1) Unanticipated problems (UPs); 2) Protocol deviations (PDs); 3) Adverse Events (AEs); 4) Serious Adverse Events (SAEs). The following AEs are expected for the study population: abrasion of the arytenoid cartilage vocal process, cartilage necrosis, cicatrix formation, consequences of failure to ventilate including death, damage to the perichondrium, development of dense or diffuse fibrosis invading the entire glottic area, emphysema, endobronchial aspiration, endobronchial intubation (hypoxemia), endotracheobronchial aspiration, epistaxis, esophageal intubation (stomach distension), excoriated membranes of the pharynx, eye trauma, fibrin deposition, formation of subglottic web, fracture-luxation of cervical column (spinal injury), fragmentation of cartilage, glottic edema (supraglottic, subglottic, retroarytenoidal), granuloma of the inner arytenoid area, infections (laryngitis, sinusitis, abscess, respiratory tract infection), inflammation, intermittent aphonia and recurrent sore throat, laryngeal fibrosis, laryngeal granulomas and polyps, laryngeal obstruction, laryngeal stenosis, laryngeal ulcers, laryngotracheal membranes and webs, membranous glottic congestion, membranous tracheobronchitis, mild edema of the epiglottis, mucosal sloughing, paresis of the hypoglossal and/or lingual nerves, perforation of esophagus, perforation of the trachea, pneumothorax, replacement of the tracheal wall with scar tissue, respiratory obstruction, retrobulbar hemorrhage, retropharyngeal abscess, retropharyngeal dissection, rupture of the trachea, sore throat, dysphagia, stricture of nostril, stridor, subglottic annular cicatricial stenosis, submucosal hemorrhage, submucous puncture of the larynx, superficial epithelial abrasion, swallowed tube, synechia of the vocal cords, teeth trauma, tissue burns, tracheal bleeding, tracheal stenosis, trauma to lips, tongue, pharynx, nose, trachea, glottis, palate, tonsil, etc., traumatic lesions of the larynx and trachea, ulcerations exposing cartilaginous rings and minor erosions at cuff site, ulcerations of lips, mouth, pharynx, ulcers of the arytenoid, vocal cord congestion, vocal cord paralysis, vocal cord ulcerations, and death.

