10.3 POPULATIONS FOR ANALYSES

An intent-to-treat (ITT) population will be defined as all adult patients whose trachea was intubated with either a EVAC-PU-ETT or PVC-ETT from one of the study kits and admitted to any adult Intensive Care Unit (ICU). Approximately 1,074 patients will be included.

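### The only analysis set requires ICU admission after tube placement, so study-tube patients who die before the ICU fall outside the insertion-complication and mortality comparisons

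*Combined protocol and SAP*

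**What the plan says.** Section 7.1.2 makes the kit the unit of randomization, and Section 9.1 treats randomization and tube placement as one event, performed under exception from informed consent. Section 6.1 then lists as criterion 4 "Admitted to the ICU and receiving mechanical ventilation". The synopsis words its inclusion criterion as intubation "for acute respiratory distress or failure resulting in ICU admission and mechanical ventilation".

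Section 10.3 defines one population, labelled intent-to-treat: adults intubated with either tube "from one of the study kits and admitted to any adult Intensive Care Unit (ICU". No safety set and no set of all patients with a study tube is defined.

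Two groups of endpoints start counting before the ICU. Section 3.3.1 lists "Airway complications at the time of tube insertion" as an immediate risk, and Sections 4, 9.2 and 10.4.4 make it the first safety item. Section 4 lists in-hospital and 6-month mortality as secondary endpoints. Section 9.3.5 names "consequences of failure to ventilate including death" among the expected adverse events.

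**The concern.** For intubations outside the ICU, being in the analysis set depends on surviving a period that begins with the assigned tube. The most severe insertion outcome, early death, removes the patient from the set in which insertion harm and mortality are compared. The set is called intent-to-treat but carries a survival condition imposed after randomization.

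This also goes against the protocol's own reasoning. Section 3.2 criticises earlier trials of subglottic suction for excluding patients after randomization. Section 5.1 keeps patients who are extubated early, on the ground that they were randomly assigned. The same ground applies to a patient who dies on the way to the ICU.

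At stake is whether the trial could show a difference between tubes in the earliest and most serious harm. A difference in early death would appear in the ICU-admitted set as no difference.

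**Working it through.** **Step 1. Does any other category in the plan hold these patients?** Take an otherwise eligible adult, intubated in the emergency department with a study tube, who dies before ICU admission.

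- Section 6.1, criterion 4: not met.
- Section 10.3: not in the intent-to-treat set.
- Section 6.3: "Screen failures are defined as participants meeting inclusion criteria" and who also meet an exclusion criterion. This patient fails an inclusion criterion and meets no exclusion, so is not a screen failure.
- Sections 8.1.1 to 8.1.4: the four inadvertent-enrolment scenarios are a minor, a pregnant woman, a prisoner and a research opt-out. None fits. If the general wording in 8.1 were stretched to cover the case, Section 8.2 would have the data removed.
- Section 2.3: the tube-placement column holds only randomization and screening. Enrolment, intubation details and adverse events start at ICU Day 1.

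No analysis category covers the patient.

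**Step 2. When does this bias a comparison?** Let f be the share of placements that die before the ICU, and m the later mortality among those who reach it. The documents give neither, so both are assumptions.

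- Mortality among all placed = f + (1 − f) × m.
- Mortality in the ICU-admitted set = m.
- With equal m in both arms, the difference among all placed = (f₁ − f₀) × (1 − m), and the ICU-admitted set shows 0.

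*Equal f in both arms, m = 0.30.* For f = 1%, 3% or 5%, mortality among all placed is 0.307, 0.321 or 0.335, against 0.30 in the ICU set. The level is understated, but the difference between arms is 0 either way.

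*Unequal f: 2% versus 4%.*

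| Later mortality m | All placed, 2% arm | All placed, 4% arm | Hidden difference | Hidden difference ÷ SE at 537 per arm |
|---|---|---|---|---|
| 0.20 | 0.216 | 0.232 | 1.6 points | 0.63 |
| 0.30 | 0.314 | 0.328 | 1.4 points | 0.49 |
| 0.50 | 0.510 | 0.520 | 1.0 point | 0.33 |

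The SE is √[(p₀(1 − p₀) + p₁(1 − p₁)) / 537]. For m = 0.30 it is √[(0.314 × 0.686 + 0.328 × 0.672) / 537] = 0.0285, and 0.014 / 0.0285 = 0.49.

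As counts, 2% and 4% of 537 are 10.7 and 21.5, about 11 versus 21 early deaths. The ICU-admitted set would show 0 versus 0.

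**Step 3. How many placements are exposed?** Section 10.2 gives about 200 emergency-department and 404 in-hospital intubations a year. The emergency-department share is 200 / 604 = 33%. The split of the 404 between ICU and ward is not given, so the exposed share lies anywhere from about 33% upward. If the 2% versus 4% applied to that 33% only, the gap among all placements would be 0.02 × 0.331 = 0.66 points. The hidden mortality difference would then be 0.66 × 0.5 to 0.66 × 0.8, or about 0.3 to 0.5 points.

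**The case against.** Five points can be made for the plan.

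**Comparability.** Allocation is concealed until the kit is used. Unless tube type changes survival to the ICU, the ICU-admitted arms remain comparable. This stands, and makes the bias conditional.

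**Mechanism.** Section 3.3.1 notes the larger outer diameter of the EVAC-PU-ETT, and a reader might infer that early deaths are likely to differ by arm. The documents do not support that. The same section expects no difference in insertion risk and says that a non-study tube will be used where the outer diameter is thought to be a problem. Those patients leave through criterion 3, and a set of patients with a study tube in place would not recover them. The diameter is a reason to look, not evidence of a difference.

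**Safety reporting.** A reader might infer that the DSMB would never see these deaths. That goes too far. Section 9.1 has data collected from randomization to discharge or death. Section 9.3.4 records reportable events from randomization onward. Section 9.4.1 allows a death associated with the device to be an unanticipated problem. Section 10.4.4 sends adverse-event tables to the DSMB without naming a population, and Section 11.1.6 leaves the data elements to the DSMB charter. Whether someone who fails criterion 4 counts as a participant for these rules is unclear; reporting is not excluded. The synopsis adds to the ambiguity, because its population paragraph speaks of a requirement for ICU admission, which a patient dying before transfer could meet.

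**Size.** A reader might take a 2-point gap in early death as a 2-point loss in 6-month mortality. It is smaller, because some of those patients would have died later anyway. Even the illustrated 11 versus 21 of 537 gives a Fisher exact p of 0.10. The argument for counting these deaths is completeness of the safety record, not power.

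**Primary analyses.** The formal safety test concerns long-term laryngeal injury, and cognition is measured at 6 months. Patients who die before the ICU could not supply either measurement. This stands. One small qualification is that the percent-of-healthy-life transformation in Section 10.4.2 is meant to retain patients who die, and these deaths would be absent from it.

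**Conclusion.** The point holds for insertion complications and for in-hospital and 6-month mortality. The plan has one analysis set; it depends on an event after randomization, and it leaves out study-tube patients who die before the ICU. This conflicts with Sections 3.2 and 5.1.

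Bias between arms requires that tube type affect survival to the ICU. If it does, the comparisons favour the worse tube; if not, only the absolute rates are understated. The size cannot be derived from the documents. The 1.0 to 1.6 points rest on three assumptions: early death of 2% versus 4% across all placements, equal later mortality of 20% to 50%, and 537 placements per arm for the counts and standard errors. They would be smaller if only emergency-department and ward placements carried the gap.

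A reader might conclude that the trial's main results are compromised. The documents do not support that: the 6-month laryngeal-injury and cognition analyses are not materially affected.

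**What to change.** In Section 10.3, add a safety and mortality set: all otherwise eligible adults in whom a study-kit tube was placed, whether or not they reached the ICU. Use it for insertion complications, device-related adverse events and serious adverse events, in-hospital and 6-month mortality, and the DSMB tables. Report by arm how many study-tube patients did not reach the ICU, and why.

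Leave criterion 4 and the ICU-admitted set in place for the target of 1,074, IVAC and VAE, quality of life and cognition. Redefining trial entry is unnecessary: early deaths would then count toward 1,074, and either the target would rise or the ICU-admitted set would fall below 537 per arm.

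The cost is a second analysis set and a short record for each extra patient (arm, insertion details, vital status). These patients should be traceable through the returned kits and mailed forms in Section 7.1.1, which says of the pilot that "these strategies allowed 100% success tracking study devices and participants". The use of data from patients who die before consent would have to be agreed with the IRB. The set would still not include failed insertions converted to a non-study tube.
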